6.0 Procedures Involved

This is a pilot randomized controlled trial involving 20 African American patients with OSA and their bed partners. Patients will be identified within 48 hours of a new diagnosis of moderate to severe OSA and planned prescription of CPAP by their providers. Patients will be randomized to a usual care arm or a couple-oriented intervention arm and complete the tasks below. All patients will receive auto-titrating CPAP machines equipped with cellular modems upon enrollment into the study. Every morning the machines will use cellular communications to upload physiologic data (CPAP adherence, applied CPAP pressure, mask leak, and residual respiratory events) to RedCap. Ecological momentary assessments (EMA) in the form of morning text message will allow patients and partners to report their sleep quality and CPAP experiences in the mornings over the first 6 weeks of enrollment.⁷⁵ Shortly after waking, patients and their bed partners will receive automated interactive text messages up to 4 times per week asking them about their sleep duration, quality, and experiences with CPAP from the prior night. Their responses will be uploaded directly into RedCap for comparison to nightly CPAP machine usage reports. Couples in the intervention arm will receive automated text messages when their CPAP usage drops below designated thresholds or when there is substantial improvement in CPAP adherence.⁵³ Mosio text messaging software will be used to automatically send and receive text messages between study participants and RedCap.

STUDY TASKS	USUAL CARE ARM	COUPLE-ORIENTED INTERVENTION ARM
Care from sleep providers	
 - Order CPAP - Counsel patient about OSA diagnosis 	
 - Order CPAP - Counsel patient about OSA diagnosis
Care from study sleep technologists	
 - Standardized review of sleep study, auto-CPAP instruction and troubleshooting, and mask-fitting with patient - Standardized phone call with patient 1 week later to answer questions and address any problems that arose - Meet with patient as needed to troubleshoot problems 	
 - Standardized review of sleep study, auto-CPAP instruction and troubleshooting, and mask-fitting with patient and partner - Standardized phone call with patient and partner 1 week later to answer questions and address any problems that arose - Meet with patient and partner as needed to troubleshoot problems
Care from experienced African American patient with OSA and bed partner (peer motivators)	
 - Two health talks moderated by African American health care providers 	
 - Two support group sessions for African American patients and their partners to assist with OSA and CPAP
Automated telehealth care	Not applicable	
 - Daily review of CPAP adherence data - Contact patient and partner when any of the following is present: no data uploaded from CPAP machine in > 72 hours, mask leak > 40L/min > 30% of night, < 4hr of use for 3 consecutive nights, machine measured AHI > 10events/hr, & 90% of pressure > 16cmH₂O.⁵⁰ - Contact patient and partner when CPAP use exceeded 4hr for 3 consecutive nights.⁵³

We expect about 55% of the participants will be women, 94% will be African American non-Hispanic, and 6% will be African American and Hispanic.

Patient demographic and medical characteristics (e.g., comorbid conditions) will be obtained directly from EpicCare. Socioeconomic status will be assessed by asking patients about their education, occupation, and income. Patient and bed partner relationship quality will be assessed using the 4-item version of the Dyadic Adjustment Scale (DAS-4), one of the most widely used measures of couple satisfaction in research and clinical practice.⁷⁶ The 6-item Zarit Burden Interview for Dementia Caregivers is one of the most widely used measures of caregiver burden.⁷⁷ OSA severity will be assessed using the apnea-hypopnea index, the time spent with oxyhemoglobin saturation < 90%, and the lowest value of oxyhemoglobin saturation each retrieved from the polysomnogram report.⁷⁸ All participants will be given an autotitrating CPAP machine that can be monitored remotely. The device will upload objective adherence data to RedCap each morning following use. **Adherence is the average nightly use of CPAP from baseline to designated follow-up times (30 days, 90 days).**

Instruments to measure OSA knowledge and beliefs, depression, sleepiness, quality of sleep, quality of life, self-efficacy to use CPAP, and degree of bed partner involvement in CPAP adherence will be completed by all study participants at **baseline, 30 days, and 90 days**. These instruments have demonstrated reliability and validity and have been used in previous

studies of OSA and CPAP adherence. Depression, a potential factor confounding the relationship between the presence of sleep apnea and CPAP adherence, will be assessed using the 9 item Patient Health Questionnaire (PHQ-9).⁷⁹ It performs well among diverse patient populations.⁸⁰ The 8-item Epworth Sleepiness Scale (ESS) measures the propensity to fall asleep in eight unique situations.⁸¹ Scores on the ESS are positively associated with OSA severity,⁸² and they improve with CPAP treatment. The 8-item short version of PROMIS Sleep Disturbance Index will be used to assess self-reported perceptions of sleep quality, sleep depth, and sleep restoration. It has greater measurement precision than the ESS and the Pittsburgh Sleep Quality Index.⁸³ The impact of sleepiness on functional status will be assessed using the 10-item Functional Outcomes of Sleep Questionnaire (FOSQ-10). Quality of life will be assessed with the 12-item Medical Outcome Survey Short Form (SF-12).⁸⁴ Sleep-related quality of life will be assessed using the Calgary Sleep Apnea Quality of Life Index (SAQLI). Self-efficacy, or confidence in one's ability to use CPAP when faced with difficulties, will be assessed using the Self Efficacy Measure in Sleep Apnea (SEMSA).

DATA ELEMENT	SOURCE

 - Patient and bed partner demographic and clinical characteristics: age, gender, race, ethnicity, socioeconomic status, comorbidities, sedative and psychoactive medications - Bed partner involvement - Bed partner burden - Patient and bed partner relationship quality - OSA severity (apnea-hypopnea index, duration of oxygen hemoglobin saturation < 90%, oxygen hemoglobin saturation nadir) - CPAP settings and proper interface - CPAP adherence - Depression - Excessive daytime sleepiness - Sleep quality - Impact of sleepiness on functional status - General quality of life - Sleep apnea-related quality of life - Self-efficacy to use CPAP 	
 - Electronic health record and questionnaire - Patient and bed partner texts about sleep quality - Zarit Burden Interview (6-item) - 4-Item Dyadic Adjustment Scale (DAS-4) - Sleep study reports from electronic health record - CPAP machine download - CPAP machine daily download - Patient Health Questionnaire 9-item Depression Scale (PHQ-9) - Epworth Sleepiness Scale (ESS) - PROMIS Sleep Disturbance Index (PSQI) - Functional Outcomes of Sleep Questionnaire short version (FOSQ-10) - SF-12 questionnaire - Calgary Sleep Apnea Quality of Life Index - Self-Efficacy Measure in Sleep Apnea (SEMSA)

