5.0 Study Intervention/Investigational Agent

5.01 Usual care arm

Patients in the usual care arm will receive standard of care in the management of OSA. Patients will receive care from their sleep provider per usual. MyChart, the patient portal of the electronic health record, will be used to send patients a link to user-friendly OSA patient education programs (Emmi; Emmi Solutions LLC.).⁵³ Within 1 week of being diagnosed with OSA and enrolled in the study, sleep technologists will meet in person with patients and provide them with their auto-titrating CPAP machine; train them on its use, upkeep, and troubleshooting; and perform personalized mask fittings. Patients will be informed that their CPAP adherence will be monitored. Every morning, CPAP adherence data will be uploaded to RedCap. Patients with CPAP technical difficulties will be encouraged to contact the sleep technologist for assistance. Patients will attend a 90-minute virtual webinar and question-answer session on hypertension management, cancer screening, or weight management at 1 and 3 months led by African American physicians with expertise in each topic.

5.01a Virtual sleep logs as ecological momentary assessments. Patients will be asked whether they would prefer to receive communications via telephone, email, text message, or a

combination. During the first 6 months of the study, patients and bed partners will receive up to 4 interactive text messages/week in the morning inquiring about the quality of their sleep, their sleep-wake patterns, symptoms attributable to OSA, perceptions regarding OSA and CPAP, what time they went to sleep, when they woke up for the final time, how they rated the quality of their sleep, and any additional comments they may have.^{70,71}

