17.0 Data Management and Confidentiality

Our study database will be stored in RedCap (<https://www.project-redcap.org>),⁹⁰ a secure, open-source software application regularly utilized by [name] research teams. RedCap runs on the MetroHealth server and therefore is HIPAA compliant, provides user-specific data access, and facilitates removal of participant identifying data prior to exporting. It also facilitates double data entry with real-time data validation and data integrity checks. Patient data will be entered directly into the RedCap. Study data will be held for 7 years following study completion. Paper records will be stored in locked filing cabinets within the Center for Reducing Health Disparities (Rammelkamp R209). Mosio will use HIPAA compliant procedures to securely send and receive data between study participants and RedCap.

Because this is a pilot study, a power calculation is not provided.

We will begin our analysis by computing descriptive statistics and using graphical representations to examine all predictor and outcome variables. For each study patient, the primary outcome will be CPAP adherence at 90 days as determined by the mean daily CPAP usage (the total number of hours of CPAP use divided by the number of days observed for the

individual). An intention to treat analytic approach will compare mean daily CPAP usage between intervention and control patients as randomized. Linear mixed effects models using random effects will be used to adjust for clustering of patients within sleep provider. Covariates (fixed effects) will include indicator variables for BMI, AHI, gender, and treatment.⁸⁹ The model assumption that the overall CPAP usage outcome is normally distributed will be tested using the Shapiro-Wilk test. If a significant departure from normality is obtained (and a suitable transformation, such as log, is not found) an alternative approach will be to use a generalized linear (e.g., Poisson regression) model for the overall adherence (CPAP usage rate). A Wald test (with robust estimate of standard error) will be used to test for an intervention effect and a corresponding 95% confidence interval for the intervention effect will be computed. If substantial variability in follow-up times are found (e.g., due to dropout and/or missed visits), a weighting approach (using weights proportional to the number of days observed for each individual in conjunction with the selected model) can be used.

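### Missing device uploads are actively checked in the intervention arm only, although those uploads are the sole stated source of the primary outcome in both arms

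*Protocol*

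**What the plan says.** Both arms receive machines with cellular modems. For usual care, section 5.01 states: "Every morning, CPAP adherence data will be uploaded to RedCap". Section 6.0 describes the same upload for all patients, says that it takes place on the morning after use, and names the daily machine download as the data source for adherence. No other source is described.

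The automated telehealth row of the section 6.0 study tasks table treats the arms differently. The intervention column lists "Daily review of CPAP adherence data" and contact with the couple for several triggers, one of which is "no data uploaded from CPAP machine in > 72 hours". The usual-care column reads "Not applicable". The text above the table agrees: "Couples in the intervention arm will receive automated text messages when their CPAP usage drops below designated thresholds".

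For usual care, section 5.01 says: "Patients with CPAP technical difficulties will be encouraged to contact the sleep technologist for assistance". The table adds "Standardized phone call with patient 1 week later to answer questions and address any problems that arose" and meetings as needed. The intervention arm has the same call, with the partner included.

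Section 17.0 computes the primary outcome as "the total number of hours of CPAP use divided by the number of days observed for the" individual patient. It also allows weights proportional to days observed. Section 6.0 defines adherence as average nightly use from baseline to 30 or 90 days.

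**The concern.** Most of the triggers in that row (low use, leak, residual events, pressure) act on how the patient uses CPAP. They belong to the treatment under test, and a difference between arms there is intended. The no-upload trigger does that too, but it also bears on whether the primary outcome is seen at all. A modem that stops transmitting in the intervention arm prompts a contact after 72 hours. In usual care no staff-initiated contact for a missing upload is described, and the patient may not know that anything has failed.

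Randomisation does not protect against outcome capture that differs by arm. Because uploads follow use, a night with no upload may be a night without CPAP or a failed transmission, and the protocol does not say how to tell them apart or how to score them. With about 10 patients per arm, a few long gaps are enough to move an arm mean.

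**Working it through.** The protocol gives no power calculation, expected gap rate or standard deviation, so there is no stated figure to reproduce. The check sets the arms side by side and then works through the two possible scorings of a night without an upload.

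**Inputs from the protocol:** 20 patients, half per arm, so 10 controls; 90 nights; outcome = hours / days observed; 1.31 h/night as the effect quoted for behavioral interventions (section 3.05).

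**Assumptions, not in the protocol:** true use of 3 to 5 h on the nights concerned, the gap rates below, and no true difference between arms in steps 2 and 3.

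1. **Comparison of arms.** Source of the outcome: daily upload in both. Staff-initiated check that the upload arrived: after 72 hours in the intervention arm, none described in usual care.

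2. **Night without an upload scored as 0 h.** Spurious difference (intervention minus usual care) = u × (g − g(1 − r)) = u × g × r, where u is true use, g the share of nights lost and r the share recovered after contact.
   - u = 4, g = 0.10, r = 1: usual care 4 × 0.90 = 3.6 h, intervention 4.0 h, difference +0.4 h.
   - The same with r = 0.5: intervention 4 × 0.95 = 3.8 h, difference +0.2 h.
   - Over u = 3 to 4, g = 0.05 to 0.20 and r = 0.5 to 1: from 3 × 0.05 × 0.5 = +0.08 h to 4 × 0.20 × 1 = +0.80 h.
   - One control at 4 h/night with the modem out for 30 of 90 nights reads 4 × 60/90 = 2.67 h. The arm mean moves by −1.33/10 = −0.13 h.

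3. **Night without an upload dropped from the denominator, the lost nights being non-use nights in usual care.** Observed mean = p × h / (p + (1 − p)(1 − q)), where p is the share of nights used, h the hours on those nights and q the share of non-use nights lost.
   - p = 0.6, h = 5 (true mean 3.0 h): q = 0.10 gives 3.0/0.96 = 3.12 h; q = 0.50 gives 3.0/0.80 = 3.75 h; q = 1 gives 5.0 h.
   - p = 0.8, h = 5 (true mean 4.0 h): q = 0.10 gives 4.0/0.98 = 4.08 h; q = 1 gives 5.0 h.
   - With full capture in the intervention arm, the spurious difference runs from −0.08 to −2.0 h. The last figure needs every non-use night to be lost.

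4. **Single-patient illustration, dropped-night reading only.** A control uses CPAP 3 h/night for 60 nights and then unplugs it for 30. True mean: 3 × 60/90 = 2.0 h. Mean over nights with an upload: 180/60 = 3.0 h, an overstatement of 1.0 h. Two such controls among 10 shift the arm mean by 2/10 × 1.0 = 0.2 h, and four by 0.4 h. Against 1.31 h that is 0.2/1.31 = 15% and 0.4/1.31 = 31%. Under the weighting option, each such patient's weight would also fall to 60/90 = 0.67.

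5. **Equal capture.** With the same capture and the same recovery in both arms, the artefact in steps 2 and 3 is 0 h.

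**The case against.** The strongest reply is that the row describes care, not data management. Telemonitoring is a named part of the intervention, a silent machine may simply be an unused one, and contacting the couple is adherence support. That stands, and it is why the alerts should not be changed. It does not remove the trigger's second effect, on whether the outcome is captured.

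Usual care is also not without oversight. Patients there are told that they are monitored. Morning texts go to both arms for at least the first six weeks, with replies to be compared with machine reports. Section 18.0 provides for monitoring of data collection and quarterly data review. These may catch some failures, but none is a timed check for a missing upload.

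A reader might infer that lost data are repaired in the intervention arm and that only the control mean is distorted. The protocol does not support this. It says that the couple is contacted, not that nights are recovered; gaps shorter than 72 hours trigger no contact in either arm; and intervention gaps may persist after contact.

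The 0.2 to 0.4 h illustration also depends on one reading of the denominator. Section 6.0 defines adherence over the span from baseline to day 90, and section 17.0 links uneven follow-up to dropout and missed visits, so days observed may mean days under follow-up. The patient in step 4 then scores 180/90 = 2.0 h, which is correct, and that error vanishes. Failed uploads scored as zero would remain. The scoring rule may be set in an analysis plan that is not shown, so its absence is not itself the criticism. The one-arm check is stated in the protocol.

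**Conclusion.** The point holds in a limited form: completeness of the primary outcome's only stated source is actively checked in one arm. The direction of any bias cannot be fixed from the protocol. Zero-scoring of failed uploads would favour the intervention; dropping unseen non-use nights would work against it. The size is unknown. The ranges of +0.08 to +0.80 h and −0.08 to −2.0 h, and the 0.2 to 0.4 h illustration, rest on assumed gap rates and on full or partial recovery in the intervention arm, and they show only what is possible. If machines store nightly use and transmit it later, the problem shrinks, but the protocol does not say that they do. The change is worth making because it is cheap and leaves the intervention untouched.

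**What to change.** Keep the intervention alerts as they are and make outcome capture the same in both arms.

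- Read the device's stored nightly use (card or full device record) at the 30- and 90-day visits. Sections 6.0 and 24.0 already have the instruments completed in person at those times.
- Make that record the source of the primary outcome, and fall back on the daily upload where no stored record can be retrieved.
- Divide by all nights from baseline to day 90, or to withdrawal, in line with the section 6.0 definition. Count confirmed non-use as 0 h, and treat failed uploads without a stored record as missing.
- Report the number and length of upload gaps by arm, which is also useful feasibility information for a pilot.

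The cost is a few minutes at each visit. Participants must bring the machine or its memory, and the fix works only if the device keeps a retrievable record. That should be confirmed before it is written in.

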7.0 Data and Specimen Banking

Not Applicable.

8.0 Sharing of Results with Subjects

Results from the study will be shared through the publication of findings in research journals and via presentation at scientific meetings. Results will be directly shared with participants upon inquiry.

9.0 Study Timelines

Participants will be enrolled from April 1, 2022 to December 31, 2022. Participants will participate in the study for 90 days. The estimated date for primary analysis to be completed will be March 1, 2023.

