4.0 Study Endpoints

Primary Endpoint: Mean CPAP adherence over 90 days

Secondary Endpoints: Mean CPAP adherence over 30 days
Patient and Bedpartner quality of sleep at 90 days
Patient and Bedpartner functional status at 90 days
Patient and Bedpartner quality of life at 90 days

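### The primary analysis is estimated to be complete 30 days before the last permitted enrollee can reach day 90 (minor)

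*Protocol*

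**What the plan says.** Protocol section 9.0 (Study Timelines) makes three statements in a row: "Participants will be enrolled from April 1, 2022 to December 31, 2022"; "Participants will participate in the study for 90 days"; and "The estimated date for primary analysis to be completed will be March 1, 2023".

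Section 4.0 sets the primary endpoint: "Primary Endpoint: Mean CPAP adherence over 90 days". Section 6.0 defines adherence as average nightly use from baseline to the 30-day or 90-day time point, and has every participant complete the questionnaires at baseline, 30 days and 90 days. The Aim 2 endpoints in section 4.0 are 90-day values, for example "Patient and Bedpartner quality of life at 90 days".

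Section 17.0 computes the primary outcome as "the total number of hours of CPAP use divided by the number of days observed" for the individual. It opens with "If substantial variability in follow-up times are found (e.g., due to dropout and/or missed visits" the case for an optional weighting, "using weights proportional to the number of days observed for each individual". Section 14.0 keeps a withdrawn participant's data up to withdrawal and lets that person keep the CPAP machine.

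**The concern.** An analysis of a 90-day outcome cannot be complete before the last participant has had 90 days. No part of the protocol calls 1 March an interim look, ends enrolment earlier, or says what happens to patients who are short of day 90 at the analysis.

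The conflict could also pass unnoticed in the primary outcome. Because the denominator in section 17.0 is the individual's own observed days, a patient cut off at day 60 still yields a complete-looking mean, over a different window from the one in sections 4.0 and 6.0. The Aim 2 loss is plainer: a late couple has no 90-day questionnaire value at all on 1 March.

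A smaller, related point does not depend on the calendar. With the same denominator, a patient who withdraws is scored only at the rate of use before withdrawal, which need not be the rate over 90 days.

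**Working it through.** **Inputs from the protocol.** Enrolment 1 April to 31 December 2022, 90 days of participation, analysis complete 1 March 2023 (section 9.0); 20 patients (sections 1.0 and 12.0), half per arm (section 2.0), so 10 per arm.

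**1. Can the stated date be reproduced?** Counting enrolment as day 0:
- Last day 90 = 31 Dec 2022 + 90 days = 31 Mar 2023.
- Gap to 1 Mar 2023 = 30 days. If enrolment counts as day 1, the last day is 30 Mar and the gap is 29 days.

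The date of 1 March does not follow from the other two statements under either convention.

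**2. Who is affected if the dates are kept?**
- Latest enrolment with a full window = 1 Mar 2023 − 90 days = 1 Dec 2022.
- Affected: those enrolled from 2 to 31 December, which is 30 of the 275 enrolment days.
- The last permitted enrollee has 31 Dec to 1 Mar = 60 days of data.

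**3. How many patients?** The protocol gives no accrual curve, so this is a range under assumptions:
- Even accrual: 20 × 30/275 = 2.2 patients (30/275 = 11% of couples without 90-day questionnaires).
- Rate falling linearly to zero: 20 × (30/275)² = 0.2.
- Rate rising linearly from zero: 20 × (1 − (245/275)²) = 4.1.
- All 20 couples enrolled by 1 December: 0.

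**4. How far does the primary mean move?** Assume, for illustration, that use falls linearly from 5 to 3 h/night over 90 days. The mean over the first n nights is then 5 − n/90.
- Full window: 5 − 90/90 = 4.00 h. Last enrollee: 5 − 60/90 = 4.33 h.
- Late enrollees have n from 60 to 89, average 74.5. Mean excess = 1 − 74.5/90 = 0.172 h.
- With even accrual and all late enrollees in one arm of 10: 0.172 × 2.18/10 = 0.04 h, a little over 2 minutes a night.
- If use is steady, the shift is 0.

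**5. Withdrawal (illustration).** A patient uses CPAP 5 h/night and withdraws at day 30.
- Section 17.0 gives 5.0 h.
- The 90-day mean lies between 5 × 30/90 = 1.67 h (use stops) and 5.0 h (use continues).
- One more such patient in one arm of 10 than in the other shifts the difference by between 0 and (5.0 − 1.67)/10 = 0.33 h.

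**The case against.** The strongest reply is that 1 March is labelled an estimate. Sections 4.0 and 6.0 fix the outcome at 90 days, and nothing says that data will be cut before follow-up ends. The natural course is that the date slips and no harm follows. Enrolment also stops at 20 couples, so 31 December is an outer limit. Section 25.0 lists 1,453 eligible patients, 40% of them African American (1,453 × 0.40 ≈ 581, period not stated), so accrual may finish before December. All of this stands. It is why the point is minor, but it does not make the three statements in section 9.0 agree.

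Three stronger readings are tempting, and the documents do not support them.

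- A reader might infer that the 90 days start at CPAP set-up, up to a week after enrolment under section 5.01, which would widen the gap. But section 6.0 has machines supplied on enrolment and counts adherence from baseline, and sections 1.0 and 9.0 fix participation at 90 days. The week in section 5.01 is a maximum.
- A reader might fault the weighting for not recovering the 90-day mean. Section 17.0 makes it optional and never claims that it does.
- A reader might take the mention of missed visits to mean that they shorten the adherence window. Section 17.0 gives them only as an example of why follow-up may vary and does not say how they enter the denominator.

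It can also be said that rules for nights after withdrawal belong in a statistical analysis plan. That is largely fair, so the withdrawal point is only an addition here.

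**Conclusion.** The dates in section 9.0 conflict by 30 days, and no day-count convention removes the conflict. That part is certain. What follows from it is conditional: only if the dates are kept do late enrollees contribute a mean over 60 to 89 days instead of 90 and lack the 90-day questionnaires.

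The number affected is about 2 of 20 under an assumed even accrual, 0.2 to 4.1 under the other two accrual shapes tried, and possibly 0. The effect on the primary mean is small, and the figure for it rests on an assumed pattern of use. The loss for Aim 2 is the more tangible one.

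A reader might conclude that the primary outcome itself is wrongly defined. The documents do not support that: the 90-day window is stated consistently in sections 4.0 and 6.0, and the fault lies in a date. Severity: minor.

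**What to change.** **Reconcile the dates in section 9.0**, in one of two ways:

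1. Set the primary analysis after the last patient's day 90, so not before 31 March 2023, plus time for data cleaning. This costs about one month or somewhat more.
2. Close enrolment by 1 December 2022. This risks fewer than 20 couples. It also puts the last day 90 on 1 March itself, so either enrolment must close earlier still or the analysis date must move to leave time for cleaning.

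The first is the simpler choice, because it protects both the sample size and the 90-day questionnaires.

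**Minor addition.** Keep the baseline-to-day-90 window of section 6.0 as the reference for section 17.0, and report observed days by arm. Add one sensitivity analysis that counts nights after withdrawal as 0 h. Label it a lower bound on the withdrawn patients' use, since they keep the machine and may go on using it. It does not bound the difference between arms in a fixed direction; that depends on which arm has the withdrawals. The cost is one extra analysis and a few sentences.
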